Pain control during and after abortion is a Society of Family Planning priority. Pain management regimens for surgical abortion can rely on local anesthetic, oral analgesics, moderate sedation, deep sedation, or a combination of approaches. While several recent studies have attempted to reduce pain with adding supplemental medications or therapies, such as nonsteroidal anti-inflammatory drugs, narcotics, anxiolytics, misoprostol, nitrous oxide, music, most studies have failed to improve pain scores. As optimal pain management has not been established, many women continuing to report moderate to severe pain during and after the procedure [1].

We propose a novel regimen of oral gabapentin administered prior to usual pain management regimens for surgical abortion. Gabapentin is used to treat neuropathic and chronic pain. Mechanism of action may include calcium channel blockade and modulation of nociceptive neurotransmitters. Clinical trials support use of perioperative gabapentin to reduce post-surgical pain in a variety of clinical settings[2]. Gabapentin is well-tolerated and inexpensive, with mild, if any, side effects. [3] In a systematic review of 22 randomized controlled trials (RCT) of multiple surgical procedures including ambulatory nasal surgery, orthopedic procedures and laparotomy, a single preoperative dose of gabapentin significantly reduced 24-hour opioid consumption[3]. Perioperative gabapentin before hysterectomy showed reduced pain scores, nausea and vomiting [4, 5] A randomized trial in the setting of cesarean showed improved pain scores and decreased pain requirements with a 600 mg dose of preoperative gabapentin [5]. Its use in the setting of abortion has never been evaluated.

We hypothesize that adding gabapentin preoperatively to current pain management regimens will reduce pain associated with surgical abortion. Additionally, we hypothesize that preoperative gabapentin will reduce perioperative nausea, vomiting and anxiety with few adverse effects.

Primary Aim: To evaluate the impact of adjunctive preoperative gabapentin on perioperative pain during uterine aspiration <15 weeks of gestation for abortion and pregnancy loss management compared to usual pain control regimens

Secondary Aims

- To evaluate the impact of preoperative gabapentin on:
 - perioperative nausea and vomiting
 - preoperative anxiety
 - use of pain medications and anti-emetics post-operatively

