opioid consumption [3]. In the setting of obstetrics and gynecology, evidence supports perioperative gabapentin before hysterectomy to reduce pain scores, nausea, and vomiting [4, 5]. Preoperative gabapentin prior to cesarean section improved pain scores at 24 hours with less need for post-operative analgesia compared to placebo [5]. In an outpatient setting similar to abortion surgery, perioperative gabapentin have been shown to decrease post-operative opioid consumption and anxiety for minor orthopedic procedures and hemorrhoidectomy [13, 14].

Innovation in pain control and reduction of anxiety, nausea and vomiting using a low cost, well-tolerated intervention could impact hundreds of thousands of women each year with potential implications for other common outpatient gynecologic procedures. We propose a novel use of oral gabapentin administered in conjunction with usual pain management regimens for surgical abortion. *Use of gabapentin in the setting of uterine aspiration has never been evaluated; however it is used routinely and successfully in several similar surgical settings as an adjunct to pain management regimens.* It is generally well-tolerated and inexpensive, with minimal side effects and few contraindications [3]. If effective, this simple adjunct to current pain regimens could expand options for the management of women worldwide undergoing surgical abortions. Other secondary outcomes such as nausea, vomiting and anxiety influence a woman's ability to return to her normal baseline level of activity and her experience of abortion in general. Our prospective meta-analysis (PMA) design will allow us to simultaneously evaluate the impact of gabapentin among different gestational ages and combined with different anesthesia regimens to determine if there is utility of this easy to use, safe adjunct therapy in differing abortion care settings.

Study Design and Methodology

Study Design: This is a randomized controlled double-blind placebo-controlled trial evaluating the impact of gabapentin given preoperatively on perioperative pain scores for women receiving uterine aspiration between 6 and 14+6 weeks gestation. This study will be a trial included in a prospective meta-analysis evaluating the use of gabapentin on perioperative pain in the abortion setting.

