Gabapentin was originally approved by the U.S. Food and Drug Administration (FDA) in December 1993, for use as an adjuvant (effective when added to other antiseizure drugs) medication to control partial seizures in adults; that indication was extended to children in 2000[19] and later approved for treating postherpetic neuralgia (In December 2004 the FDA granted final approval to a generic equivalent to Neurontin made by the Israeli firm Teva. It was originally synthesized to mimic the chemical structure of the neurotransmitter GABA. The mode of action of gabapentin is believed to be through its binds to the alpha 2 delta subunit of the DRN voltage dependent calcium channels. This causes decreased entry of calcium into the nerve endings, resulting in decreased release of nociceptive neurotransmitter (glutamate, substance p, noradrenaline). Other proposed mechanisms of action include the binding to NMDA receptors, sodium channel receptors, monoaminergic receptors, and opioid receptors

Overall, Gabapentin is an incredibly safe drug. The most common side effects of its use includes dizziness, somnolence, fatigue, ataxia, peripheral edema, nystagmus, nausea and vomiting, asthenia, headache, weight gain, amblyopia, however most of these are associated with chronic usage. Other extremely rare side effects include: DRESS (drug reaction with eosinophilia and systemic symptoms), multi-organ hypersensitivity, withdrawal seizures (if given for epilepsy), suicidal behavior and ideation, neuropsychiatric reactions in pediatric patients (3-12 yo), and sudden death.

Drug Interactions are rare and mild. Maalox or other aluminum or magnesium hydroxides decreases bioavailability of gabapentin by 20% if given at same time. Additionally, when used

with hydrocodone or morphine, gabapentin may decrease the AUC. Abuse and withdrawal potential is low. The drug is almost entirely metabolized through the renal metabolism where it is eliminated unchanged in the urine, thus dosage adjustments are needed for patients with renal impairment. The half-life for the medication is 5-7 hours with a 2 hour time to peak plasma concentration.

Study intervention groups:

Group 1/Placebo: Usual perioperative pain management protocol PLUS placebo orally 1-2 hour prior to procedure

Group 2/Gabapentin: Usual perioperative pain management protocol PLUS 600mg Gabapentin administered orally 1-2 hour prior to procedure.

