Women undergoing a procedure who meet study inclusion criteria and complete informed consent will be eligible for participation. *Randomization* will be done using computer-generated random numbers (randomization.com) in variable blocks of 8 and 10. *Allocation* concealment will be maintained by identically labeled sealed sequentially numbered opaque pill containers. Gabapentin and placebo tablets will be indistinguishable by appearance, thus maintaining blinding for participants and assessors. To maintain double *blinding* for both investigators and participants, an individual not associated with study conduct will create the randomization sequence and allocation containers. The randomization assignments will only be revealed at the point of data analysis or if an interim assessment is needed.

Enrollment:

After the final perioperative clearance, the individual will be randomized and receive their method allocated by the clinic nurse. The study staff will review the enrollment questionnaire that includes demographic questions. Following completion of the questionnaire, the participant will wait before moving to our procedure room (this will occur approximately 1-2 hour after nursing review and receipt of the study intervention). Prior to initiating the procedure, study staff will administer the preoperative questions. The physician will then complete the uterine aspiration while the study staff remains outside of the operative room. Immediately following the procedure, the study staff will then administer the immediate post-operative questions and follow the participant to the recovery room to complete the remaining questions assessed at 5 minutes, 10 minutes, 30 minutes and at discharge. When the discharge questions are complete, the

participant will receive a \$20 gift card and instructed to expect a follow-up call the following day.

Follow-up:

On the day following the procedure (approximately 24 hours after the procedure), study staff will call the participant to complete the follow-up questions. On completion of the questions, an additional \$10 will be transferred to the gift card.

Withdrawals, losses and deviations:

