Randomization to study method will occur after completion of all intake forms and consent, immediately before the pill is to be taken, thus reducing the possibility of withdrawal after randomization. Primary outcome measures and most secondary outcome measures will be assessed immediately before, during or after the abortion procedure, thus any loss to follow-up will be limited to those who consent to, but change their mind while waiting for their procedure. Based on current clinical practice at this clinic, withdrawal after consent is extremely rare. Our secondary outcomes assessed post-operatively after discharge will be collected via the phone. We will maximize completion of these assessments through the following steps: participants will be told beforehand about the telephone contact following the procedure, a cellular telephone number will be collected and tested at the clinic, a secondary phone number and email will be collected as a backup, participants will be given a contact number for the study coordinator should they have any challenges with receiving a phone calls, and participants will receive an additional \$10 sent to their gift-card following the completion of their phone assessment.

Data Collection/Outcome measurements:

Outcome measures and baseline variables are described in Table 1.

Primary study outcome

Our primary outcome measure will be pain score using an 100-mm visual analog scale (VAS) measured 5 minutes after removal of the speculum.

Secondary Outcomes:

We will also be measuring pain on the 100-mm VAS preoperatively immediately prior to the procedure, after the procedure, 10 minutes and 30 minutes following the procedure and at discharge. Nausea, using a VAS, and vomiting will be assessed preoperatively immediately prior to the procedure and post operatively at 10 minutes, 30 minutes and at discharge. Anxiety prior to the procedure will be measured using the preoperative state trait anxiety inventory. Side effects will be assessed using a checklist prior to discharge. We will also be contacting participants on post-operative day 1 to assess pain, nausea, vomiting, side effects and general satisfaction with the procedure (on a 5-point scale). The quantity and type of medications used perioperatively and post-operatively including medications used at home in the 24 hours post-operatively will be abstracted from the clinical record and assessed on the phone.

Baseline Characteristics and covariates:

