2. Opiate Pain medication (including oxycodone, Percocet, oxycontin)	 ₀ NO  ₁ YES	 ₀ NO  ₁ YES	 ₁	 ₂	 ₃	Type: _____
3. Other pain medication	 ₀ NO  ₁ YES	 ₀ NO  ₁ YES	 ₁	 ₂	 ₃	Type: _____

HEALTH HISTORY

11. Have you ever been pregnant before (prompt: regardless of outcome)?

₀ NO ₁ YES → Answer questions a-e below

- a) How many times? _____
- b) Number of miscarriages or ectopic pregnancies _____
- c) Number of C-sections? _____
- d) Number of vaginal deliveries? _____
- e) Number of abortions? _____ (if 0 → 12)
- f) Number of medical abortions: _____
- g) Number of surgical abortions: _____
- h) Number under local anesthesia: _____

12. Now I will ask you a couple questions about your medical history

Do you have any of the following conditions			Follow-up questions if YES
1	Anxiety	 NO  YES	b. Do you take medication for it?  NO  YES c. Type of medication
2	Depression	 NO  YES	b. Do you take medication for it?  NO  YES c. Type of medication
3	Other psychiatric condition (such as bipolar, schizophrenia, PTSD)	 NO  YES	b. Other condition _____ c. Do you take medication for it?  NO  YES d. Type of medication

13. Have you ever been sexually or physically assaulted?

- NO
- YES, Sexually Assaulted
- YES, Physically Assaulted
- YES, Both sexually and physically assaulted

From Chart Abstraction:

Gestational Age: _____

Height: _____

Weight: _____

Anesthetic Regimen: ₁ LOCAL ₂ IV Moderate Sedation ₃ Deep Sedation

Medications Used:

Time of speculum placement: : AM/PM

Time of speculum removal: : AM/PM

Procedural Complications?

\square_0 NO \square_1 YES: Description:

Preop Assessment

Time: ___ ___ : ___ ___ AM/PM

For these questions we are going to ask you to make a hash mark on a line.

For example, let's say you are asked how much you like Oreo cookies:

How much do you like Oreo cookies? (make a hash mark on the line)

very

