You answer the question by making a hash mark on the line according to how much you like or dislike Oreo cookies.

If you liked Oreo cookies a lot, then you might make a hash mark on the line like so:

very
little

very
much

If you liked Oreo cookies more than life itself(!), then you might make a hash mark on the line like so:

very little _____ |

very
much

If you hated Oreo cookies, then you might make a hash mark like so:

very
little

very
much

If you thought Oreo cookies were just "OK," then you might make a hash mark like so:

very
little

very
much

The idea is that if you like Oreo cookies, you make a hash mark on the line closer to the phrase "very much;" the closer you make the hash mark, the more you are saying you like Oreo cookies. If you don't like Oreo cookies, you make a hash mark on the line closer to the phrase "very little;" the closer you make the hash mark, the more you are saying you don't like Oreo cookies.

1. Make a hash mark on the line to indicate how nervous you feel about the surgery you are about to have.

NOT
NERVOUS _____

VERY NERVOUS

2. Make a hash mark on the line to indicate how nervous you feel about the pain you will experience during your procedure.

NOT
NERVOUS _____

VERY
NERVOUS

3. Make a hash mark on the line to indicate how much pain you expect to have during your abortion procedure.

NO
PAIN _____

WORST PAIN
IN MY LIFE

4. Make a hash mark on the line to indicate how much pain you have waiting for your procedure to start.

NO
PAIN _____

WORST PAIN
IN MY LIFE

5. Make a hash mark on the line to indicate how much nausea you currently have

NO
NAUSEA _____

WORST NAUSEA
I HAVE EVER HAD

Have you vomited since you received your study medication?

NO YES

State Trait Anxiety Inventory[1]

Read each statement and select the appropriate response to indicate how you feel right now, that is, at this very moment. There are no right or wrong answers. Do not spend too much time on any one statement but give the answer which seems to describe your present feelings best.

		Not at all	A little	Somewhat	Very much so
1	I feel calm	1	2	3	4
2	I feel secure	1	2	3	4
3	I feel tense	1	2	3	4
4	I feel strained	1	2	3	4
5	I feel at ease	1	2	3	4
6	I feel upset	1	2	3	4
7	I am presently worrying over possible misfortunes				
8	I feel satisfied	1	2	3	4
9	I feel frightened	1	2	3	4
10	I feel uncomfortable	1	2	3	4
11	I feel self confident	1	2	3	4
12	I feel nervous	1	2	3	4
13	I feel jittery	1	2	3	4
14	I feel indecisive	1	2	3	4

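### Nausea is a named secondary hypothesis, but no pre-pill nausea score appears in the supplied text, so the planned t-test gives up precision that one intake item could recover

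*Combined protocol and SAP*

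**What the plan says.** All references are to the combined protocol and SAP.

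- **Hypothesis (opening summary).** "we hypothesize that preoperative gabapentin will reduce perioperative nausea, vomiting and anxiety with few adverse effects". The Secondary Aims list nausea and vomiting first, and later "use of pain medications and anti-emetics post-operatively".
- **Population (Study Design).** "women receiving uterine aspiration between 6 and 14+6 weeks gestation".
- **Dosing (Study intervention groups).** "600mg Gabapentin administered orally 1-2 hour prior to procedure"; placebo has the same timing.
- **First nausea score (Secondary Outcomes).** "Nausea, using a VAS, and vomiting will be assessed preoperatively immediately prior to the procedure", then at 10 minutes, 30 minutes and discharge. The Enrollment section says of the move to the procedure room: "this will occur approximately 1-2 hour after nursing review and receipt of the study intervention". The preoperative questions follow that wait.
- **Draft Questionnaire, Preop Assessment.** The nausea item reads "Make a hash mark on the line to indicate how much nausea you currently have". The vomiting item beside it asks about the time since the study medication, which confirms that the form is filled in after dosing.
- **Baseline data (Baseline Characteristics and covariates).** Nausea and vomiting are not listed. Medications taken at home are listed, with no drug class excluded. Item 10 of the Draft Questionnaire, however, names only ibuprofen, opiates and other pain medication.
- **Analysis (Analytic Plan).** T-tests for continuous and chi-square tests for categorical secondary outcomes. Baseline characteristics are to be examined for interaction or confounding, but no model is named.

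**The concern.** Every participant is having a uterine aspiration for a pregnancy of up to 14+6 weeks, and some may well arrive already nauseated; the documents give no prevalence. Nausea present before dosing will carry through to the post-operative scores. Without a pre-pill measure, that between-woman variation cannot be removed from the comparison.

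The only score labelled preoperative is taken after randomization and after the drug has had 1-2 hours to act; the protocol puts peak plasma concentration at 2 hours. Adjusting for it would remove part of any early drug effect on nausea.

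What is at stake is the precision of one secondary comparison, and the ability to tell nausea that preceded the pill from nausea that followed it. The second matters because the protocol also lists nausea and vomiting among gabapentin's side effects. A pre-pill value cannot be recovered once the pill has been taken.

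**Working it through.** **The plan's own figure.** Study Size and Power gives 96 women, SD 26 mm, a 15 mm difference in pain, 80% power and p = 0.05; the Recruitment section gives equal allocation.

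n per arm = 2 × (1.960 + 0.842)² × 26² / 15² = 47.2, rounded up to 48, so 96 in total. This reproduces (two-sided). Power at 48 per arm is 80.7% by the normal approximation and 79.9% by the t-test. No figure is stated for nausea.

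**Inputs for nausea.** From the documents: 48 per arm and an unadjusted t-test. Assumed: SD 25 mm (range 20 to 30 mm), and correlation r between the pre-pill and a later nausea score of 0.3, 0.5 or 0.7. The documents give neither.

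**Detectable difference, unadjusted.** From the non-central t with 94 df, 48 per arm detects 0.578 SD at 80% power: 0.578 × 25 = 14.4 mm. At SD 20 and 30 mm it is 11.6 and 17.3 mm.

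**With a pre-pill covariate.** ANCOVA multiplies the residual SD by √(1 − r²). The equivalent gain in sample size is 1/(1 − r²). The one degree of freedom spent on the covariate is ignored.

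| r | √(1 − r²) | Detectable difference at SD 25 mm | 1/(1 − r²) | 96 women worth about |
|---|---|---|---|---|
| 0 (unadjusted) | 1.000 | 14.4 mm | 1.00 | 96 |
| 0.3 | 0.954 | 13.8 mm | 1.10 | 105 |
| 0.5 | 0.866 | 12.5 mm | 1.33 | 128 |
| 0.7 | 0.714 | 10.3 mm | 1.96 | 188 |

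**Chance imbalance.** The SE of a difference in mean pre-pill nausea is 25 × √(2/48) = 5.1 mm, so the 95% range is ±1.96 × 5.1 = ±10 mm. That is the gap in the baseline score. With equal SDs before and after, the shift it causes in the post-operative difference is the gap times r: 10 × 0.3 = 3 mm, 10 × 0.5 = 5 mm, 10 × 0.7 = 7 mm at the 95% limit. The t-test's standard error already allows for this variation.

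**The case against.** The strongest reply is that nothing here is an error. Randomization keeps the unadjusted comparison unbiased in expectation, and its standard error covers chance imbalance. Nausea is a secondary outcome that did not drive the sample size, and at r = 0.3 the gain is only from 14.4 to 13.8 mm. All of this stands, and it limits the point to precision.

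Three further replies:

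- **Table 1** is said to describe the baseline variables and is not in the supplied text. The absence of a pre-pill item therefore rests on the Secondary Outcomes section, the baseline list and the draft forms. This stands as a caveat.
- **Existing covariates.** Gestational age and home medication will be collected, and baseline characteristics will be examined for confounding. These are only proxies for nausea, and no adjustment model is given.
- **Misuse of the Preop score** is not planned; it is listed as an outcome. That is correct. The wording still invites it: the Secondary Aims name preoperative anxiety level as a patient characteristic for subgroups, although anxiety is measured on the same post-pill form.

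A reader might infer from item 10 that home anti-emetic use is not collected. The documents do not support that, because the baseline list includes home medication without excluding any class. What remains is a draft form that does not prompt for what the text plans to collect.

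A reader might also infer that women continuing a usual anti-emetic will be counted as new post-operative users. No counting rule is stated, and the plan is to record the quantity and type of medication, so this cannot be asserted.

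**Conclusion.** The point holds as a cheap improvement, not as a flaw in validity. In the supplied text, nausea is first measured after dosing, so no baseline nausea score is available and the planned t-test carries pre-existing nausea as noise. At an assumed SD of 25 mm, a pre-pill covariate would lower the detectable difference from about 14.4 mm to between 13.8 mm (r = 0.3) and 10.3 mm (r = 0.7). The size of the gain depends entirely on a correlation that the documents do not give.

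Reading this as bias in the nausea result, or as a 10 mm distortion, would go too far. The 10 mm is a chance gap in the baseline score; the corresponding shift in the outcome is about 3 to 7 mm and is already within the stated uncertainty. The primary pain outcome is not affected.

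**What to change.** 1. Add to the intake form one nausea VAS line and a yes/no question on vomiting that day, both completed before the pill is taken.
2. Fix that timing explicitly. The section on withdrawals, losses and deviations has all intake forms completed before randomization, whereas the Enrollment section describes the questionnaire after randomization and receipt of the allocation.
3. State in the Analytic Plan that post-operative nausea scores are compared by ANCOVA on the pre-pill score, and that the post-pill Preop score is an outcome and is never used as a covariate.
4. Add an anti-emetic prompt to draft item 10, so that the form matches the planned collection of home medication.

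The cost is about one minute of intake by staff already present, one or two sentences in the analysis section, and a form amendment to be aligned with the other sites in the prospective meta-analysis.
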